#### **9.5.1.2 Change from baseline in WHO Ordinal Scale for Clinical Improvement at Day 15, Day 22 and Day 29**

Baseline for WHO Ordinal Scale for Clinical Improvement will be the last available record prior to first dose of study medication.

For subject who die, WHO Ordinal Scale for Clinical Improvement will be set to the worst possible outcome (8 – death) for the following planned timepoints to give deaths unfavorable value in the analysis. For subjects who are discharged early, or are otherwise having missing values, following timepoints use data from multiple imputation. Details for the imputation will be given in the SAP.

WHO Ordinal Scale for Clinical Improvement will be summarized using frequencies and percentages by treatment group and timepoint. Also change from baseline will be summarized.

Change from baseline will be analyzed as ordinal response using proportional odds logistic regression. Analysis will be performed separately for each timepoint (Day 15, Day 22, Day 29). Proportionality of odds will be tested and if the proportionality assumption does not hold, then non-proportional odds model will be fitted. Model will include treatment as fixed effect and study site, gender, remdesivir use (No/Yes), dexamethasone use (No/Yes) and WHO Ordinal Scale for Clinical Improvement at baseline as covariate. Odds ratio, 95% confidence interval and p-value for the treatment difference will be presented. Distribution of change from baseline will be plotted in stacked bar plot by treatment group and time point.

Proportional (or non-proportional) odds model will be performed only using the imputed data to include all subjects in the analysis.

Additionally, descriptive statistics (n, mean, standard deviation, median, minimum and maximum) will be summarized for absolute values and change from baseline by treatment group and visit.

Additionally, change from baseline will be analyzed using mixed model for repeated measures (MMRM) including treatment, visit and treatment-by-visit interaction as fixed effects and study site, gender, remdesivir use (No/Yes), dexamethasone use (No/Yes) and WHO Ordinal Scale for Clinical Improvement at baseline as covariate. The resulting F-tests will be based on Kenward-Roger's adjusted degrees of freedom. Least squares means, standard errors, 95% confidence intervals and p-values for treatments and treatment differences at each visit will be presented.

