2.2 Secondary Objectives

The secondary objectives/endpoints on this study are:

Controlled Quality Management Document		
	Sponsor: Veru Inc.	Protocol Number: V3011902
STATISTICAL ANALYSIS PLAN. PHASE 2-3-4		

1. The proportion of subjects that are alive without respiratory failure at Day 15, Day 22, and Day 29. Day 29 is the key secondary endpoint. Respiratory failure is defined as endotracheal intubation and mechanical ventilation, extracorporeal membrane oxygenation, high-flow nasal cannula oxygen delivery, noninvasive positive pressure ventilation, clinical diagnosis of respiratory failure with initiation of none of these measures only when clinical decision making is driven solely by resource limitation
2. Days in Intensive Care Unit (ICU)
3. WHO Ordinal Scale for Clinical Improvement change from baseline to Day 15, Day 22, and Day 29.

Patient State	Descriptor	Score
Uninfected	No clinical or virological evidence of infection	0
Ambulatory	No limitation of activities	1
	Limitation of activities	2
Hospitalized, Mild disease	Hospitalized, no oxygen therapy	3
	Oxygen by mask or nasal prongs	4
Hospitalized, Severe disease	Non-invasive ventilation or high-flow oxygen	5
	Intubation and mechanical ventilation	6
	Ventilation + additional organ support – pressors, Renal Replacement Therapy (RRT), Extracorporeal Membrane Oxygenation (ECMO)	7
Death	Death	8

4. Days on mechanical ventilation
5. Days in hospital

Controlled Quality Management Document		
	Sponsor: Veru Inc.	
	Protocol Number: V3011902	
STATISTICAL ANALYSIS PLAN. PHASE 2-3-4		

6. Proportion of subjects that die on study at Day 15, Day 22, and Day 29.
7. Change from baseline in viral load (baseline to Day 9).

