6.11.5.2 Days in ICU

‘Days in ICU’ will be summarized using descriptive statistics (n, mean, standard deviation, median, minimum and maximum) by treatment group.

‘Days in ICU’ will be the number of days in ICU up to Day 60. In this analysis the worst possible endpoint will be assigned to those subjects who died at any time up to Day 60. For subjects who died the days in ICU will be set to 60. Even for those who were never in the ICU. If

Controlled Quality Management Document			
	Sponsor:	Veru Inc.	
	Protocol Number:	V3011902	
STATISTICAL ANALYSIS PLAN. PHASE 2-3-4			

subject did not report any days in the ICU then their days will be set to zero except for those who died.

Same analysis will be performed in subgroups for region, standard of care and WHO Ordinal Scale at baseline.

A sensitivity analysis will be performed using the actual number of days in ICU. If subject was never in the ICU then days in ICU will be set to 0 even if subject died.

Treatment comparison will be based on analysis of covariance (ANCOVA) model including treatment as a factor, and study site (or country or region), remdesivir use (No/Yes), dexamethasone use (No/Yes) and WHO Ordinal Scale strata used in randomization as covariates. Treatment difference, standard error, 95% confidence interval and p-value will be presented.

Example SAS codes for the analysis are as follows:

```
proc mixed data=XXX order=internal;
  class trt01pn site remdesivir dexamethasone;
  model response=trt01pn site remdesivir dexamethasone whostrata /
    ddfm=kr;
  lsmeans trt01pn / cl diff;
  ods output tests3=tests lsmeans=lsmeans diff=diffs
  run;
```

6.11.5.3 WHO Ordinal Scale for Clinical Improvement change from baseline to Day 15, Day 22, and Day 29

WHO Ordinal Scale for Clinical Improvement will be summarized in frequency table by visit and treatment group.

Additionally, response status for each subject will be defined based on WHO Ordinal Scale for Clinical Improvement. This analysis will compare subjects that have WHO score 0 or 1 (responder) on the visit to subjects who have WHO score ≥ 2 (non-responder) on the visit.

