Baseline for WHO Ordinal Scale is the last available record up to and including Day 1. If subject was discharged from the hospital prior to Day 15, 22 or 29 and WHO Ordinal Scale for Clinical Improvement is not collected or record is otherwise missing at those timepoints then the last available observation before or at the time of death/discharge will be carried forward. If subject dies then following time points will be set to the worst possible outcome (score=8).

Controlled Quality Management Document		
	Sponsor:	Veru Inc.
	Protocol Number:	V3011902
STATISTICAL ANALYSIS PLAN. PHASE 2-3-4		

The number and percentage of responders will be summarized by treatment group and visit.

Responders will be analyzed using similar logistic regression model except not planning multiple imputation as the above algorithm provides responder status for all subjects.

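### The SAP replaces the protocol's multiple imputation of missing WHO scores with carry-forward, which at a 0–1 responder cut can fix recovered subjects as non-responders

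*SAP*

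**What the plan says.** Protocol 9.5.1.2 analyses change from baseline in the WHO score at Days 15, 22 and 29. Deaths are scored 8 at later time points. For everyone else without a value: "For subjects who are discharged early, or are otherwise having missing values, following timepoints use data from multiple imputation". It adds: "Proportional (or non-proportional) odds model will be performed only using the imputed data to include all subjects in the analysis", and says the same of the MMRM.

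SAP 6.11.5.3 turns the endpoint into a responder analysis: "This analysis will compare subjects that have WHO score 0 or 1 (responder) on the visit", with 2 or more as non-response. For a discharged subject without a score at the visit, the SAP's rule is that "then the last available observation before or at the time of death/discharge will be carried forward". The logistic model is then similar to that for the primary endpoint, "except not planning multiple imputation as the above algorithm provides responder status for all subjects".

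The visible text of SAP section 9 lists three changes: the randomisation strata, the move from MMRM to a responder analysis, and the Holm procedure. It does not mention missing WHO scores.

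Four other places determine which scores exist:
- Protocol 8.5 to 8.7 place the Day 15, 22 and 29 WHO assessment at the visit, or on the day of discharge if that is earlier.
- Protocol Appendix B marks the score at Days 22 and 29 without a discharge exception.
- Protocol 8.8 collects the score by phone at Days 45 and 60.
- SAP 6.2.10 maps discharge records to the closest scheduled post-baseline time point.

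**The concern.** The two documents give different rules for the same missing data, and the difference matters more because of the SAP's cut-off. A score taken on leaving hospital describes the subject that day, not one to four weeks later. At a cut between 1 and 2, a carried score of 2 is non-response whatever happens afterwards. A carried 3 means "Hospitalized, no oxygen therapy", which cannot describe someone who has been discharged. Subjects who withdraw while in hospital are likewise held at their last in-hospital score.

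At stake are the responder rates at the three visits, the treatment comparison built on them, and its standard error, since a carried value enters the model as if it had been observed.

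**Working it through.** **1. The rules side by side**

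| Item | Protocol 9.5.1.2 | SAP 6.11.5.3 |
|---|---|---|
| Outcome | Ordinal change from baseline; MMRM in addition | Responder, 0–1 versus 2 or more |
| After death | 8 | 8 |
| Discharged, no visit score | Multiple imputation | Last score before or at discharge |
| Otherwise missing | Multiple imputation | Last available score |
| Score collected at the visit | Used | Used |

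The protocol leaves the details of imputation to the SAP, but it states the method itself.

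**2. When the SAP rule misclassifies**

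Three conditions must all hold: no score at the visit, a last score of 2 or more, and true recovery to 0 or 1 by the visit. SAP 6.2.9 shows the behaviour for a different endpoint: a subject discharged at 2 on Day 5 is held at 2 to Day 60.

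SAP 6.11.5.1 uses a similar carry-forward after discharge for survival without respiratory failure. There the cut is 0–4 versus 5–8, so a discharge score of 2 or 3 is classed as response, and imputation is kept where vital status is unknown. The harm here comes from carry-forward together with the 0–1 cut.

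**3. A second route to the same result**

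Under SAP 6.2.10 a discharge score can become a visit value without any carry-forward. The WHO score's scheduled post-baseline days are 15, 22, 29, 45 and 60. If those are the time points meant, a Day 5 discharge score maps to Day 15, and a Day 26 discharge score maps to Day 29 (3 days away, against 4 from Day 22).

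**4. Size, by illustration**

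The documents give no rate or power for this endpoint, so there is no planned figure to reproduce. Inputs: 140 and 70 subjects (SAP section 4) and two-sided 0.05 (SAP 6.11). Assumed true Day 29 responder rates: 60% on VERU-111 and 40% on placebo.

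Let h be the share of true responders recorded as non-responders. It is the product of the share whose last score was 2 or more and the share of those with no visit score; for example, 50% × 50% = 25%. The observed rate is the true rate × (1 − h).

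Power = Φ[(d − 1.96 × SE0) / SE1], where d is the difference in observed rates p1 − p2, SE0 = √[p̄(1 − p̄)(1/140 + 1/70)], p̄ = (140p1 + 70p2)/210, and SE1 = √[p1(1 − p1)/140 + p2(1 − p2)/70].

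With h = 0: p̄ = 0.533, SE0 = 0.0730, SE1 = 0.0717, so Φ[(0.20 − 0.1431)/0.0717] = Φ(0.793) = 79%.

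| h, both arms | Observed rates | Difference | Power |
|---|---|---|---|
| 0% | 60% v 40% | 20 points | 79% |
| 25% | 45% v 30% | 15 points | 55% |
| 50% | 30% v 20% | 10 points | 33% |
| 75% | 15% v 10% | 5 points | 16% |

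Unequal shares change the direction:
- h = 50% on VERU-111 and 25% on placebo: 60% × 0.50 = 30% and 40% × 0.75 = 30%. The true 20-point difference disappears.
- h = 25% on VERU-111 and 50% on placebo: 60% × 0.75 = 45% and 40% × 0.50 = 20%. The difference is inflated to 25 points.

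**The case against.** The strongest reply is that the rule is narrower than it looks. It applies only when no visit score exists; a score collected at Day 29 is used. Day 29 is a full visit, Appendix B schedules the WHO score there without exception, and Protocol 8.10 asks for every effort to complete the later visits after early discontinuation. A subject discharged at 0 or 1 counts as a responder. All of this stands. A reader might infer that the Day 29 result mostly measures the discharge-day score, or that early discharge as such is counted as failure. The documents support neither: they give no discharge-day scores, and Protocol 8.5 to 8.7 and Appendix B leave open who is scored after discharge.

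It can also be said that the protocol's imputation served models the SAP has replaced, that section 9 discloses the replacement of the MMRM, and that SAP 6.11.5.3 says openly that imputation is not planned. So nothing is concealed. But changing the analysis model does not require changing the missing-data rule, and section 9 is where such a departure should be listed.

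Finally, imputation has limits. If discharged subjects have no Day 15 to 29 scores by design, it relies heavily on the Day 45 and 60 calls and on an untestable assumption. That is a real cost, but carry-forward makes a stronger assumption, namely no change after discharge, and ignores those calls.

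**Conclusion.** The concern holds as a conflict between protocol and SAP, with a foreseeable misclassification whenever the last score is 2 or more and no visit score follows. The departure is missing from the visible text of SAP section 9.

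Its size cannot be derived from the documents. The fall in power from 79% to between 55% and 16% rests on assumed true rates of 60% and 40% and on equal hiding of 25% to 75% of true responders. A reader might infer a one-directional loss of power or a bias against VERU-111. Neither is established, because the unequal cases above go both ways.

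The consequence is limited. SAP 6.11.7 puts only days in ICU and days on mechanical ventilation in the Holm-tested family, so this endpoint carries no controlled claim, and the Day 60 mortality analysis is untouched. It is worth correcting, but it does not threaten the trial's main conclusion.

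**What to change.** In SAP 6.11.5.3:
- Keep every score observed at Day 15, 22 or 29, and score 8 from death onward.
- Multiply impute the remaining scores, as the protocol states, with an ordinal or longitudinal model using treatment, randomisation stratum, earlier scores, discharge status and the Day 45 and 60 phone scores. Pool by Rubin's rules.
- State that the mapping in SAP 6.2.10 does not turn a discharge-day score into the observed value of a later visit.
- Keep carry-forward as a sensitivity analysis.

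Reconcile Protocol 8.5 to 8.7 with Appendix B on scoring after discharge, and list any remaining departure from Protocol 9.5.1.2 in SAP section 9.

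The cost is moderate. The imputation code in SAP 6.11.1 handles one binary Day 60 response and uses no WHO scores over time, so a new model must be written and checked. Where Day 15 to 29 scores are absent, its results will depend on the Day 45 and 60 data, and the report should say so. No new data collection is needed for the analysis change.

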6.11.5.4 Days on mechanical ventilation

Mechanical ventilation is defined as subject having ‘Intubation and mechanical ventilation’ or ‘Ventilation + additional organ support – pressors, RRT, ECMO’.

‘Days on mechanical ventilation’ will be summarized using descriptive statistics (n, mean, standard deviation, median, minimum and maximum) by treatment group.

‘Days on mechanical ventilation’ will be defined using two different algorithms similarly to ‘Days in ICU’.

‘Days on mechanical ventilation’ will be analyzed using the same methodology as for ‘Days in ICU’ and the same sensitivity analysis will be performed.

6.11.5.5 Days in hospital

‘Days in hospital’ will be summarized using descriptive statistics (n, mean, standard deviation, median, minimum and maximum) by treatment group.

‘Days in hospital’ will be defined using two different algorithms similarly to ‘Days in ICU’.

‘Days in hospital’ will be analyzed using the same methodology as for ‘Days in ICU’ and the same sensitivity analysis will be performed except the subgroup analyses will not be performed.

6.11.5.6 The proportion of subjects that die on study at Day 15, Day 22, and Day 29.

The number and percentage for all-cause mortality will be summarized by treatment group and visit.

These endpoints will be analyzed using the same methodology as for the primary endpoint (separate analysis will be performed for each visit):

- Multiple imputation + logistic regression model
- Risk differences between treatment groups (using identity link function).

Controlled Quality Management Document			
	Sponsor:	Veru Inc.	
	Protocol Number:	V3011902	
STATISTICAL ANALYSIS PLAN. PHASE 2-3-4			

6.11.5.1 Change from baseline in viral load (baseline to Day 9)

Descriptive statistics (n, mean, standard deviation, median, minimum and maximum) will be summarized for absolute values and change from baseline by treatment group and visit. For viral load post-BL time points for summary and analysis will be 'Last On-Study' and 'Day 9 only'.

Change from baseline in viral load will be analyzed using the same methodology as for 'Days in ICU' but including also viral load at baseline as covariate.

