#### **9.5.1.5 Mean change from baseline in Viral load to Day 9**

The mean change in viral load from baseline to Day 9 will be assessed.

Descriptive statistics (n, mean, standard deviation, median, minimum and maximum) will be summarized for absolute values, and change from baseline by treatment group.

Change from baseline will be analyzed using the same methodology as for change from baseline in WHO score ([section 9.5.1.3](#)).

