6.2.8 Inexact Values

In the case where a variable is recorded as “> x”, “ \geq x”, “< x” or “ \leq x”, a value of x will be taken for analysis purposes.

For pharmacokinetic data values below lower limit of quantification (LLOQ) will be handled as follows in summary tables:

- If value collected before first dose of study treatment then set to 0.
- If value collected on or after the first dose of study treatment then set to LLOQ/2.

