6.12 Pharmacokinetic Analyses

Pharmacokinetic concentration data will be summarized using descriptive statistics (n, mean, standard deviation, median, minimum and maximum) at each time point. Also CV%, geometric mean, geometric SD and geometric CV% will be presented.

Geometric mean is calculated as

$$\mu_g = \sqrt[n]{x_1 x_2 x_3 \dots x_n},$$

where n is the number of observations and x_i are the observed data. This can be expressed also in the following form

$$\mu_g = \exp\left(\frac{\sum_{i=1}^n \ln x_i}{n}\right),$$

which is easier for the practical calculation. This would simply be the exponent of the arithmetic mean from logarithmically transformed data.

Geometric standard deviation (SD)

Geometric SD is calculated as

$$\sigma_g = \exp\left(\sqrt{\frac{\sum_{i=1}^n (\ln x_i - \ln \mu_g)^2}{n}}\right).$$

This would simply be the exponent of the arithmetic standard deviation from logarithmically transformed data.

Geometric coefficient of variation (CV)

Geometric CV is calculated as

$$CV_g = \sqrt{e^{(\ln \sigma_g)^2} - 1},$$

where $\ln \sigma_g$ is the arithmetic standard deviation from logarithmically transformed data.

Geometric CV can be multiplied by 100 if CV displayed in percentage.

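### Viral load change is analysed by an untransformed ANCOVA with no unit, scale or log transformation stated; if the data are in copies/mL, a few values would dominate and much power could be lost

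*SAP*

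**What the plan says.** The protocol (9.5.1.5) states the endpoint as a mean: "The mean change in viral load from baseline to Day 9 will be assessed". For the method it says: "Change from baseline will be analyzed using the same methodology as for change from baseline in WHO score". In Protocol 9.5.1.2 that method is a proportional odds model plus an MMRM. The cross-reference printed with the sentence is to 9.5.1.3, which is days on mechanical ventilation.

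The SAP takes a different route, in the viral load section (the second one numbered 6.11.5.1): "Change from baseline in viral load will be analyzed using the same methodology as for" days in ICU, with baseline viral load added as a covariate. The method it borrows is in SAP 6.11.5.2: "Treatment comparison will be based on analysis of covariance (ANCOVA) model including treatment as a factor, and study site (or country or region), remdesivir use". The example code there fits PROC MIXED to the response with no transformation. The viral load summaries are arithmetic: "Descriptive statistics (n, mean, standard deviation, median, minimum and maximum) will be summarized for absolute values and change from baseline by treatment group and visit".

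Three other SAP provisions bear on this:

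- **Log-based summaries** are specified only for drug concentrations (6.12): "Also CV%, geometric mean, geometric SD and geometric CV% will be presented".
- **Results reported as below x** follow the general rule in 6.2.8: "a value of x will be taken for analysis purposes".
- **Variables already derived in the source data** are, by default, not derived again (6.2).

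SAP section 9 lists three departures from the protocol: the randomisation strata, the WHO score analysis and the Holm procedure. The new viral load method is not among them.

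**The concern.** Viral load in copies/mL typically spans orders of magnitude. A linear model of raw change on raw baseline is then fitted to strongly right-skewed data, and the treatment difference is set largely by the few subjects with the highest loads. A proportional reduction that is clear on the log scale can disappear in that noise.

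Nothing in the plan would prevent this if copies/mL is what reaches the analysis dataset. The SAP does use logarithms for drug concentrations, so their absence for viral load cannot be read as a document-wide convention left unsaid.

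At stake is the plan's only virological efficacy endpoint, for a drug whose rationale in the protocol introduction is in large part antiviral. Leaving the scale open also leaves a choice that could be made after the data are seen.

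**Working it through.** **No figure of the plan to reproduce.** The documents give no SD, effect size or power for viral load. The only stated power (above 92%) is for mortality and has no bearing here. All viral load inputs below are therefore assumptions, shown over a range.

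**Inputs**
- Two-sided alpha 0.05 (SAP 6.11) and 2:1 allocation of 210 subjects, 140/70 (SAP 4).
- Assumed: 110/55 subjects with Day 9 data; correlation 0.6 between log10 baseline and log10 Day 9; equal log10 SD at both times; true difference of half an SD; a 1 log10 fall on placebo.
- Left out: site and medication covariates, deaths before Day 9, and values below quantification (taken up below).

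**Log10 scale, by formula.** The residual SD after adjusting for baseline is SD × √(1 − 0.6²) = 0.8 SD. The standard error of the difference is 0.8 SD × √(1/110 + 1/55) = 0.8 SD × 0.1651 = 0.1321 SD. The ratio is 0.5/0.1321 = 3.785, and power is Φ(3.785 − 1.960) = Φ(1.825) ≈ 0.966. The SD cancels, so this holds for every row below.

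**Raw scale, by simulation** (3,000 trials per row). The same data are analysed by ANCOVA of raw change on raw baseline.

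| log10 SD | Difference (log10) | Power, log10 scale | Power, raw copies |
|---|---|---|---|
| 0.5 | 0.25 | about 96-97% | about 75% |
| 0.75 | 0.375 | about 96-97% | about 57% |
| 1.0 | 0.5 | about 96-97% | about 40% |
| 1.5 | 0.75 | about 96-97% | about 23% |
| 2.0 | 1.0 | about 96-97% | about 16% |

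Repeat runs agree to within about two percentage points. The share of power kept is 75/96 = 0.78 at SD 0.5, 57/97 = 0.59 at SD 0.75 and 40/97 = 0.41 at SD 1.0. In this set-up, more than half is lost only from an SD of about 1.0 upward.

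**Larger effects.** At 110/55, with SD 1.0 and a difference of 1.0 log10, power is 100% on the log scale and about 82-84% on the raw scale. With SD 0.75 and a difference of 0.75 it is 100% and 95%.

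**A second set-up** uses 140/70, correlation 0.5, and an effect sized for 80% power on the log scale. Raw power is then 72%, 51%, 38%, 28%, 15% and 12% at SDs of 0.25, 0.5, 0.75, 1.0, 1.5 and 2.0.

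**Who drives the estimate** (same set-up, 210 subjects). On the raw scale, the five largest squared residuals hold about 59%, 79%, 89% and 96% of the residual sum of squares at SDs of 0.5, 0.75, 1.0 and 1.5. On the log scale the share is 16%.

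**Type I error.** With no true difference, the raw-scale test rejects in 4.6%, 3.5% and 3.0% of trials at SDs of 0.5, 1.0 and 1.5 (140/70), so it is not inflated.

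**Values at a quantification limit.** Setting censored values to the limit (SD 1.0 or 1.5, effect sized for 80%) lowers log-scale power to 69-76%. Raw power is 16-27%. The log scale remains better.

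**The case against.** The strongest reply is that the documents never say the analysis is on the copies scale. No unit is given, so copies, log10 copies and Ct all fit the text. Because source-derived variables are not re-derived, results supplied on a log scale would be analysed as supplied, and there would be no problem. This stands: a reader might infer that a raw-copies analysis is planned, but the documents support only that the scale is unspecified.

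A reader might also infer that most of the power is bound to be lost. That does not follow. The loss depends on an SD and an effect size that the documents do not give, and it is modest for a small SD or a large effect.

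Nor do the calculations support calling the test invalid or liable to produce a false antiviral claim: type I error is at or below the nominal level. Confidence interval coverage away from the null was not examined.

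It would also be wrong to say that results below quantification have no rule, since SAP 6.2.8 covers them. Medians are to be reported and subject-level values listed, so the data would not be wholly uninformative on any scale.

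Materiality is limited too. Viral load is the last-listed secondary endpoint and is not in the Holm family (SAP 6.11.7).

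What remains is that an inferential analysis is pre-specified without its scale, and that its literal wording performs worse on the common unit of copies/mL.

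**Conclusion.** The point holds conditionally. SAP 6.11.5.1 applies an untransformed linear ANCOVA to viral load change, and neither document fixes the measurement scale. If results are in copies/mL, a few subjects dominate the estimate, and power falls from about 96-97% to between 75% and 16% for log10 SDs of 0.5 to 2.0. Those figures rest on 110/55 subjects, correlation 0.6 and a difference of half an SD, none of which the documents supply. If results are log10 copies or Ct, nothing is lost.

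The harm is lost precision and an unstable estimate on one secondary endpoint. The primary mortality test and the error-controlled secondary claims are unaffected.

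One part needs no assumption: the SAP replaces the protocol's WHO-score method with ANCOVA and does not record this in section 9. That is a documentation gap, and it is not evidence about the scale.

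**What to change.** In the viral load part of SAP 6.11.5:

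1. State the unit in which results are supplied.
2. State that results in copies/mL are log10-transformed before change is computed, with log10 baseline as the covariate. Results already supplied as log10 copies or Ct are analysed as supplied.
3. Apply the existing rule of SAP 6.2.8 (below x set to x) before the transformation.
4. Report the treatment difference in log10 units and, back-transformed, as a geometric mean ratio.

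In SAP section 9, record that ANCOVA replaces the protocol's WHO-score method for this endpoint. Correct the cross-reference in Protocol 9.5.1.5 at the next amendment.

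The cost is a few sentences and one derived variable. It needs no further subjects, time or alpha, provided it is settled before unblinding.
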